4. *Communication Variables:* The attitudes coupled with Likert-type scales that identified perceptions of communication associated with surgical decisions from the initial study.
5. *Trust:* The Medical Mistrust Index [93]

6-month Telephone Interview

1. Health Status: repeat SF-12
2. Communication Variables as above
3. Patient satisfaction cancer care including the choice of treatment

12-month Telephone Interview. Will repeat 6 month items. To fully assess the importance of lung resection surgery within 4 months of diagnosis, we will determine whether each patient, surgical and nonsurgical, remains alive one year. We will re-administer the SF-12 survey and satisfaction measures by telephone to survivors. We will find patients by maintaining a linkage file that includes best telephone number file, stored separately from original survey information. If the patient is not located at the original number, we will seek current information from the office of their physician or through local phone listings. If a patient surrogate answers the phone, we will seek the patient's availability and clinical status in the conversation with the surrogate.

4. *Interventions – Each site will identify a physician leader to serve as a liaison to the CCE.*
 - A. Cancer Communication – Because of the gaps between documented outcomes of lung cancer surgery and patient communication barriers identified in our recent work, our communication intervention will focus on improving presentation of risk information and confirmation of understanding [13]. Given good post operative outcomes [45, 94] in most patients with significant comorbidities, and the doubling of one-year mortality in our prospective “no surgery” group, patients’ perceptions of worse one-year prognosis with surgery are either misinterpreted or poorly explained. In lung cancer only one-half of patients comprehend proposed treatment within 3 days of their clinical visit and only 40% expressed satisfaction with communication [60]. Moreover, effective communication skills, such as active listening and the teach-back method, which can assist education and confirm understanding are used infrequently in clinical care. For example, Schillinger demonstrated that only 12% of new concepts had confirmation (teach back) by the clinician in encounters for diabetes [59]. Several studies have documented difficulty understanding numbers and calculations, particularly the idea of risk [95].

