- D. Co-morbidity educational checklist – The co-morbidity check list will be designed to address the seeming over interpretation of co-morbid states in decisions against surgery by African-American patients or their physicians (II and VII). Derived from the retrospective chart review, this checklist will be used to help inform physicians' decisions in patients who do not have absolute contra-indications for surgery. Overall results of the retrospective chart review will be delivered at the beginning of designated MTOP conferences at each study site or at a mutually agreeable meeting that includes the whole lung cancer care team. For African-American study patients randomized to intervention who are identified as having dropped out of care per the definition in section 1, the most recent physician in the specific patient's chain of care, will be given that patient's co-morbidity list via the CCE. This list will serve as a reminder that decisions for African-American patients have been different and will be designed to attenuate the subjective use of co-morbid states to justify decisions against lung resection surgery.

5. *Outcome Measures*

Primary Outcome. Whether or not patients undergo lung resection surgery represents the main study outcome. We will conform to the 4 month standard used in the SEER database. To ascertain the result, we will first call patients' physicians to determine whether surgery occurred within the designated time frame. Given the possibility that individual patients could seek other opinions and receive surgical care elsewhere, when appropriate, we will ask the patient, or a family member (if the patient is dead or unavailable), whether surgery was performed by someone other than the index physician. If surgery has not occurred, we will ask for reasons. Through appropriate consent, we will retain the option of confirmatory medical records review. For secondary analyses, we will record surgeries that occur beyond the 4 month threshold.

Secondary Outcomes.

1. One year, post-enrollment survival in surgical and non-surgical groups
2. Satisfaction of patients that received interventions compared to those who did not
3. Patients' perceptions of communication for those patients that received intervention compared to those who did not
4. SF-12 scores at baseline, 6 months post-enrollment and 12 months post enrollment

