Lung Cancer Surgery: Decisions Against Life Saving Care - The Intervention

NCT01687738

Protocol Date: May 13, 2011

Most Recent IRB Approval Date: March 29, 2016

Lung Cancer Surgery: Decisions Against Life Saving Care - The Intervention

STATISTICAL ANALYSES

Outcome Measures

Primary Outcome. Whether or not patients undergo lung resection surgery represents the main study outcome. We will conform to the 4 month standard used in the SEER database. To ascertain the result, we will first call patients' physicians to determine whether surgery occurred within the designated time frame. Given the possibility that individual patients could seek other opinions and receive surgical care elsewhere, when appropriate, we will ask the patient, or a family member (if the patient is dead or unavailable), whether surgery was performed by someone other than the index physician. If surgery has not occurred, we will ask for reasons. Through appropriate consent, we will retain the option of confirmatory medical records review. For secondary analyses, we will record surgeries that occur beyond the 4 month threshold.

Secondary Outcomes.

1. One year, post-enrollment survival in surgical and non-surgical groups
2. Satisfaction of patients that received interventions compared to those who did not
3. Patients' perceptions of communication for those patients that received intervention compared to those who did not
4. SF-12 scores at baseline, 6 months post-enrollment and 12 months post enrollment

6. Data Analysis:

Our current plan includes:

Descriptive statistics (means, standard deviations, frequencies, proportions, correlations, and graphical displays) will be computed for all study variables at baseline and post-baseline. The distribution of all outcome variables will be assessed to determine if distributional assumptions are valid. Descriptive statistics will be obtained for all the variables overall and by race and site. Statistical methods for addressing each of the specific aims of the study are detailed in this section. Since several statistical tests are planned, there is the possibility of incurring spurious results if we do not correct for multiple comparisons. All tests are based on a 2-sided alpha of 0.05.

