The main outcome of interest is whether patients undergo surgery is a dichotomous variable, either yes or no. We will compute proportions to estimate the probability of surgery for blacks and whites and compute 95% confidence intervals for the proportions. Since the main outcome is dichotomous, logistic regression for clustered data (clustered within sites) using multiple predictors will be used to assess the simultaneous effect of predictors on the outcome.

Specific Aim 1. To maximize surgical rates for all patients with stage I and II, non-small cell lung cancer who do not have absolute contraindications for lung resection surgery.

hypothesis 1a. a cancer communicator who utilizes active listening and teach-back methods during discussions about lung cancer surgery with newly diagnosed, early stage patients will increase the rate of surgery in Caucasian and African-American patients who do not suffer absolute contra-indications for lung cancer surgery compared to usual care

The primary outcome variable, surgery yes or no, will be compared in the control group randomized to usual care, to the intervention group randomized to the cancer communicator. Bivariate analyses will be performed using the surgical outcome as the dependent variable. Independent variables in these analyses will include important group, demographic variables

such as age, race, marital status, household income, health insurance, gender, and education as well as measures of trust, patient satisfaction, functional status, self-reported health, comorbid illness, perceptions of communication, and the communication intervention. We will use bivariate analyses, including correlations and chi-square tests of association, to make preliminary assessments of the relationships between study variables, overall and by race.

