The modeling approach will be to initially define as large a maximum model as possible using main effects only (initially no interactions). Preliminary analyses of similar data indicates that the sample size combined with a sufficient number of events (surgery yes) will allow upwards of 30-35 main effects to be included in the model with good reliability for estimation and inference. The generalized estimating equations (GEE) for binary outcomes will be used to fit logistic regression models for clustered data [102]. The primary outcome variable is binary, surgery yes or no, and outcomes of patients clustered within the same site (and/or MD) are expected to be correlated. GEE will allow fitting a logistic regression to the binary outcome while adjusting for the effect of clustering within the same site (and/or MD). As stated previously, independent variables in these analyses will include important demographic variables such as age, race, marital status, household income, health insurance, gender, and education as well as measures of trust, patient satisfaction, functional status, self-reported health, comorbid illness, perceptions of communication, and the communication intervention. The significance of each of the main effects while adjusting for all other effects from the maximum model will be assessed. A backwards elimination approach will, initially, remove effects with a p-value of greater than 0.10. This excludes selected predictors forced predictors into the model (forced predictors include group, comorbid illnesses and selected baseline scores). The reduced model will be refit. Variables have p-values greater than 0.05 will then be removed. The final reduced main effects model, including forced predictors will be refit. Selected interactions will be considered for inclusion into the final reduced main effects model. For the secondary outcomes, survival analysis techniques will be used to assess the one year, post-enrollment survival in surgical and non-surgical groups. Kaplan-Meier curves will be generated. Linear regression models for repeated measures (discrete) outcomes using GEE will be used to assess patient satisfaction of patients that received interventions compared to those who did not, for patients' perceptions of communication for those patients that received intervention compared to those who did not, and for SF12 scores at 6 months post-enrollment and 12 months post enrollment. Covariates will include baseline, group, and other covariates listed above.

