
hypothesis 1b. the communication intervention will be more effective in patients who score lower in measures of health literacy

Using the logistic regression analyses for clustered data as noted above, the interaction effects of health literacy, S-TOFHLA scores, and intervention group will be tested in all models. . S-TOFHLA scores will be tested as a continuous variable and also, separately, as a dichotomous variable comparing those categorized as inadequate or marginal literacy with those categorized as adequate literacy [103]. Cumulative pre-intervention surgical rates will be compared at all sites with post-intervention rates using Pearson's chi-square test. Post-intervention rates will be compared using test of proportions and changes in proportions from baseline will be compared between surgical and nonsurgical groups using appropriate methods. To determine if the post-intervention rate approaches maximal surgical rates, we will identify patients with high risk co-morbidities, above the age of 80, and need for pneumonectomy or multiple lobectomy in the "no surgery group", subtract this sum from the denominator then re-calculate the surgical rate. We will analyze the secondary specific aim, To measure the effect of the intervention on patients' perceptions of communication and satisfaction with care, by dichotomizing these variables and replacing surgery as the dependent variable in chi-square and logistic regression models as described under the specific aim above.

Specific Aim 2. To reduce the documented difference in lung resection surgery and mortality between African-American and White patients with early stage, non-small cell

lung cancer.

hypothesis 2a. giving physicians who make lung cancer surgery decisions data relating co-morbidity to surgical outcomes will reduce racial differences in surgery

hypothesis 2b. using a real time lung cancer registry to provide physicians race-specific feedback about their surgical treatment of early stage lung cancer patients will reduce racial differences in surgery

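### The adjusted model for surgery within 4 months includes patient satisfaction, which is first measured at 6 months and is itself an intervention outcome

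*SAP*

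**What the plan says.** SAP section 6, hypothesis 1a, defines a large main-effects GEE logistic model for surgery. After the demographic variables, its list of independent variables continues "as well as measures of trust, patient satisfaction, functional status, self-reported health, comorbid illness, perceptions of communication, and the communication intervention". No time point is attached to any of these. Terms with p above 0.10 are dropped first, then those above 0.05. The terms exempt from removal are described thus: "forced predictors include group, comorbid illnesses and selected baseline scores". Satisfaction is not named among them.

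The model is used again. Hypothesis 1b begins "Using the logistic regression analyses for clustered data as noted above", hypothesis 2c refers back to the Aim 1 regressions, and the before/after analysis in Aim 3 adjusts for the Aim 1 variables.

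Protocol E.3 lists the baseline questionnaire as demographics, SF-12, health literacy, communication variables and trust. Satisfaction first appears as item 3 of the 6-month telephone interview, "Patient satisfaction cancer care including the choice of treatment", and is repeated at 12 months. On the outcome window, Protocol E.5 says "We will conform to the 4 month standard used in the SEER database".

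Secondary outcome 2 is "Satisfaction of patients that received interventions compared to those who did not". Under hypothesis 1b, the SAP also dichotomises satisfaction and puts it in place of surgery as the response in the same models.

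Separately from the regression, hypothesis 1a plans a direct arm comparison: "The primary outcome variable, surgery yes or no, will be compared in the control group randomized to usual care, to the intervention group".

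**The concern.** As listed, satisfaction is recorded after the outcome it would help to predict, and the item asks about the treatment chosen, which is close to the outcome itself. The SAP also expects the communicator to change it. Conditioning on a variable that both arm and outcome influence undoes the protection of randomisation for the arm coefficient.

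Backward elimination is a poor safeguard. It tends to keep a variable that surgery itself influences, which is one of the two conditions for bias.

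The adjusted and unadjusted results for hypothesis 1a could then disagree, and the SAP does not say which one decides.

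Missing data add a second problem. Surgery status can be obtained from the physician, the patient "or a family member (if the patient is dead or unavailable"), so it can be known without a patient interview. Satisfaction cannot. The SAP states no missing-data rule, and a complete-case fit would drop patients whose primary outcome is known.

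**Working it through.** **Timing.** The outcome window is 4 months from diagnosis; the interviews are 6 and 12 months from enrolment. The 6-month call would fall inside the window only if diagnosis were dated more than 6 − 4 = 2 months after enrolment.

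**The plan's own figure.** SAP section 7 gives 80% power for 0.63 to 0.69 with N = 496, one-sample test, two-sided 0.05.
- Null SE = √(0.63 × 0.37 / 496) = 0.0217. Alternative SE = √(0.69 × 0.31 / 496) = 0.0208.
- Power = Φ[(0.06 − 1.96 × 0.0217) / 0.0208] = 80.0%.

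This reproduces, but it compares all patients with the previous study. It says nothing about the adjusted arm comparison.

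**Formula for the bias.** Let satisfaction be S = a·arm + s·Y + N(0,1), with Y = 1 for surgery. By Bayes' rule, the log odds of Y given arm and S equal the log odds given arm plus the log ratio of the normal densities of S at Y = 1 and Y = 0. That log ratio is s·S − a·s·arm − s²/2. The arm coefficient therefore shifts by −a·s, so

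adjusted OR = true OR × exp(−a·s).

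Same-sign effects lower the odds ratio, opposite signs raise it, and there is no bias if either is zero.

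**Simulation.** Inputs: N = 496 from the SAP, split 248 per arm (assumed; no ratio is stated); control rate 63% (the previous study's overall rate, used as an assumption); satisfaction removed and the model refitted if p > 0.05. There were 4,000 replicates per row, with no other covariates, clustering or missing data. All values of a and s are assumptions.

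True odds ratios: (0.69/0.31)/(0.63/0.37) = 1.31 for 63% vs 69%, and (0.75/0.25)/(0.63/0.37) = 1.76 for 63% vs 75%. The first borrows the SAP's one-sample difference as an arm difference. The second is assumed. Unadjusted power is 29% and about 83% respectively.

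| a, s | exp(−a·s) | Null: adjusted OR | Null: rejection | Satisfaction kept (null) | 63% vs 69%: adjusted OR, power | 63% vs 75%: adjusted OR, power |
|---|---|---|---|---|---|---|
| 0, 0.5 | 1.000 | 0.996 | 4.8% | 100% | not run | not run |
| 0.1, 0.3 | 0.970 | 0.965 | 5.9% | 90% | 1.27, 24% | 1.71, 77% |
| 0.2, 0.2 | 0.961 | 0.969 | 5.3% | 57% | 1.27, 24% | 1.72, 78% |
| 0.3, 0.3 | 0.914 | 0.913 | 6.9% | 90% | 1.21, 17% | 1.63, 68% |
| 0.3, 0.5 | 0.861 | 0.854 | 12.3% | 100% | 1.13, 10% | 1.53, 54% |
| 0.5, 0.5 | 0.779 | 0.781 | 22.6% | 100% | 1.02, 5% | 1.37, 33% |
| −0.3, 0.5 | 1.162 | 1.164 | 12.6% | 100% | 1.53, 57% | 2.05, 94% |

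In the last row, 12.1 of the 12.6 percentage points of null rejection favour the communicator. At (0.2, 0.2) the simulated odds ratio lies closer to 1 than the formula gives, because satisfaction is eliminated in 43% of trials.

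A separate run of 2,000 replicates, without elimination, agreed. Null rejection was 5.6%, 7.0% and 26.0% at a = s = 0.2, 0.3 and 0.5, and power for 63% vs 75% was 75.8%, 65.2% and 32.9%.

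**The case against.** **Hypotheses 1b and 2c concern interactions.** If a and s are the same in all patients, the shift −a·s is constant and leaves an arm-by-modifier term alone. In a simulation with a true interaction of 0.30, adjusted and unadjusted estimates were 0.315 and 0.312 at (0.3, 0.3), and 0.303 and 0.305 at (0.5, 0.5). This stands. The interaction moves only if a or s differs by literacy or race. For example, with s = 0.5 and a = 0.2 in one group and 0.6 in the other, it shifts by −(0.6 − 0.2) × 0.5 = −0.20 in log odds.

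**Aim 3 is a before/after comparison.** The retrospective chart review described in Protocol D is collected in aggregate, with no satisfaction interview. If those are the earlier data, satisfaction could not enter that model. This also stands, and is itself a reason to take it off the list.

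**A baseline item may exist.** The instrument appendix is not available, and the SAP says the satisfaction models adjust for a baseline value. None is listed, however, so the text needs correcting either way.

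**The regression may be meant as predictor modelling, with the unadjusted test as the real comparison.** That reading is fair, and the unadjusted test is unaffected. But group is forced into the regression, so an adjusted arm effect will be produced, and the SAP does not rank the two.

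**The size is assumed.** True. No document gives a or s, and with up to 30–35 main effects, overlap with trust or perceptions of communication could change whether satisfaction is kept. At the two smallest non-zero pairs, null rejection is only 5–6%.

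**Conclusion.** The point holds for the adjusted communicator odds ratio in hypothesis 1a. The plan as written conditions a randomised comparison on a variable that, by the listed instruments, is measured after the outcome and that the plan itself treats as an effect of the intervention.

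That mismatch is certain from the text. The bias is conditional: it needs satisfaction to depend on both arm and surgery, which the secondary aim and the wording of the 6-month item make plausible. Its direction follows the signs of the two effects. Over the non-zero pairs examined, a true odds ratio of 1 becomes anything from 0.78 to 1.16. For 63% vs 75%, power of about 83% becomes anything from 33% to 94%; the high figure reflects upward bias rather than a gain.

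For hypotheses 1b and 2c, bias in the interaction needs the further assumption that a or s varies by literacy or race. For Aim 3, no bias has been calculated. The point should be fixed before analysis; it does not undermine the unadjusted comparison or the stated power.

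**What to change.** - Delete patient satisfaction from the covariate list of every surgery model that uses the Aim 1 covariates: hypotheses 1a, 1b and 2c, and the Aim 3 adjustment.
- State that perceptions of communication and SF-12 enter those models only as baseline-questionnaire values.
- Analyse 6- and 12-month satisfaction and perceptions of communication only as outcomes.
- If the questionnaire does contain a baseline satisfaction item, name it and allow only that value. If not, correct the statement that the satisfaction models adjust for baseline.

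The growth models for hypotheses 2a and 2b need no change, since their stated predictors do not include satisfaction.

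The cost is a text edit to the SAP, with no new data and no change in sample size.

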E. Prospective Study: All sites will begin recruiting patients by the beginning of study Month 13. As most cancer programs have at least rudimentary patient tracking and navigation, this degree of usual care will serve as the control. All providers will receive the co-morbid illness educational checklist at all sites and will receive monthly data concerning surgical rates by comorbid condition and race. Patients will be randomized to either usual care or a more intense communication intervention delivered by a trained cancer communication educator as described below. Since we are building on the methods of our prior cohort study, pretesting of recruitment methods and study instruments can proceed quickly before randomization. Lung cancer surgery rates in the control groups will be compared to historical controls at the individual sites to account for a passive effect of the registry and educational checklist. As care registries and data compilation by race is a mandate of the HITECH portion of the American Recovery and Reinvestment Act, we don't believe that it's ethical to deny any group access to the registry. Given the flat rate of lung cancer surgery and persisting racial gap documented for over a decade in datasets of national scope [7, 36, 38], historical controls for this portion of the study are justified.

1. Inclusion and Exclusion Criteria for Patients

We will enroll patients who meet these criteria: (1) age 21 years or greater; (2) a probability of 60% or higher of a lung lesion being malignant as calculated by Bayesian analysis derived from clinical and radiographic criteria or, alternatively, biopsy proven disease; and (3) the patient has received a clinical classification of stage I or II disease. By "clinically classified", we mean using all studies including CT scans, PET scans, bone scans, mediastinoscopy, and / or any study or procedure performed short of thoracotomy.

We will exclude patients from this study for 3 reasons: (1) incarceration / ward of the state status, (2) severe cognitive impairment, (3) absolute contraindications by pulmonary function testing, or (4) Non-English speaking. Hispanic patients represent less than 4 percent of lung cancer patients in North Carolina restricting our ability to document an intervention effect.

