Note that we do not propose enrolling patients based on tissue diagnosis alone. Any patient diagnosed with non-small cell lung cancer by bronchoscopy or needle biopsy who has been staged with I or II disease will automatically be included. Obtaining tissue prior to open surgery is not always possible. To assess these patients, several reports have reliably demonstrated the use of Bayesian logic to calculate the probability that a lung lesion is malignant [89-92] has published the most comprehensive compendium of likelihood ratios for clinical and radiographic findings; this study will serve as the basis for our preoperative analysis. Because of the difficulty of obtaining a diagnosis in small peripheral lung lesions with less invasive approaches, many patients proceed to surgery with only an estimation of "odds" for cancer. When these individuals decide to have surgery, they generally agree to 1 operation with a 2-step approach: (1) thoracoscopic biopsy and then (2) if frozen sectioning of the biopsy reveals cancer, the appropriate resection procedure. Some individuals, particularly those who suffer from advanced chronic obstructive lung disease, will refuse surgery if the preoperative diagnosis is not certain.

For the patients who agree to this 1-surgery, 2-step approach, there is no time between tissue diagnosis and definitive surgery. Therefore, these patients need to be enrolled based on their preoperative probabilities.

2. *Patient Recruitment*

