The SF-12 physical and mental component scores will be converted to 0 – 100 scales and utilized as the dependent variable. Baseline scores will be compared first to 6 month scores then 12 month scores using paired t-tests. Generalized linear mixed models for repeated measures data will be constructed in a similar manner as the logistic regression models described above; however, surgical status, race, and comorbid conditions will be forced predictors in these model.

Note that interim analyses regarding specific aims 1 and 2 will be performed at the end of study year 2 then annually. If statistically significant benefits in care are documented on surgical rates and reduction in disparities, the study will be terminated and workshops and individual training sessions of the communication methodologies will be initiated for the care teams at all the study sites.

7. Sample Size

Power computations are computed for post-intervention comparison of proportions. The project anticipates enrolling 496 patients into the study due to constraints on budget, patient availability, and study duration. Thus, we compute the minimal effect size we can detect with statistical power of 80% for our primary aim, AIM 1, using the specified sample size. In computing the effect size, we specify our main outcome as the probability of undergoing surgery for all patients post-baseline as compared to the probability for all patients in the previous study because all groups will receive the data registry and feedback interventions.

Let p_1 be the proportion all patients who undergo surgery in the present study and $p_0 = 0.63$ be the proportion of patients who underwent surgery in the previous study. Using a one-sample test of proportion with 496 subjects overall and significance level of 0.05, we have 80% power to detect a minimally important difference (increase) in surgical rate of $p_0 = 0.63$ to $p_1 = 0.69$. With a sample size of 159 for blacks, we have 80% power to detect an overall increase from $p_0 = 0.55$ (as measured in the previous study) to $p_1 = 0.66$ with significance level of 0.05. With a sample size of 337 for whites, we have 80% power to detect an overall increase from $p_0 = 0.66$ (as measured in the previous study) to $p_1 = 0.73$ with significance level of 0.05.

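### Clinical stage and tissue-proven status are known at entry but are not named or forced in the models, so the surgical versus non-surgical comparisons of survival and SF-12 may be confounded.

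*SAP*

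**What the plan says.** **Entry facts.** Protocol section E.1 requires that "the patient has received a clinical classification of stage I or II disease". It admits patients by one of two routes: biopsy-proven disease, or a calculated malignancy probability of 60% or more. Both facts must therefore be settled before enrolment.

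**Link to surgery.** Section E.1 says that some patients, especially those with advanced chronic obstructive lung disease, "will refuse surgery if the preoperative diagnosis is not certain". It also describes a single operation in which resection follows only if the frozen section shows cancer. Section C says that registry surgery rates are too high because they leave out patients without tissue who refused surgery or were lost from follow-up.

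**Covariates.** SAP section 6, hypothesis 1a, lists seven demographic items, "as well as measures of trust, patient satisfaction, functional status, self-reported health, comorbid illness, perceptions of communication, and the communication intervention". That makes 14 named items including the intervention. The forced predictors are group, comorbid illnesses and selected baseline scores. Other terms can be removed at p > 0.10 and then at p > 0.05.

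**Other analyses.** One-year survival by surgical status is described with Kaplan-Meier curves, and no covariates are named for it. The Aim 4 SF-12 models force surgical status, race and comorbid conditions. Aim 3 refers to multiple clinical characteristics without defining them.

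**The concern.** Surgical status is not randomised. A patient enrolled on probability alone may have a benign lesion, not be resected, and then be counted in the non-surgical group. Some other patients without tissue decline surgery because the diagnosis is uncertain. Stage II plausibly carries a worse prognosis than stage I whatever the treatment. The surgical and non-surgical groups may therefore differ in entry route and stage, and forcing comorbidity does not correct for either. These influences can act in opposite directions, so the net direction of the bias cannot be predicted.

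At stake are the survival outcome and hypotheses 4a and 4b, which claim better function after surgery. The racial gap in surgery is a second, conditional case: it is affected only if stage or entry route differs by race among enrolled patients.

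**Working it through.** **1. The plan's own figure.** SAP section 7 states: "Using a one-sample test of proportion with 496 subjects overall and significance level of 0.05, we have 80% power to detect" a rise from 0.63 to 0.69. With "All tests are based on a 2-sided alpha of 0.05":

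- SE under the null = √(0.63 × 0.37 / 496) = 0.0217; SE under the alternative = √(0.69 × 0.31 / 496) = 0.0208.
- Power = Φ[(0.06 − 1.96 × 0.0217) / 0.0208] = 80.0%.

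The figure reproduces and is not in dispute. It is a comparison with a historical rate, so the arm comparison needs its own base case.

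**2. Arm effect.** The protocol says "Patients will be randomized to either usual care or a more intense communication intervention" without a ratio, so I assume 248 per arm. I take a control rate of 0.63 and an intervention rate of about 0.746 (log odds ratio 0.548, SE 0.196), the difference with roughly 80% power. Unadjusted power is 79.6%.

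I then add two binary covariates, using the large-sample information matrix of the logistic model. Power = Φ(estimate / SE − 1.96). The documents give no shares or effects, so these are assumptions: stage II in 20–30% and no tissue in 20–40%.

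| Odds ratios for surgery (stage II, no tissue) | Adjusted power |
|---|---|
| 0.7, 0.7 | 80.0–80.1% |
| 0.5, 0.5 | 80.9–81.4% |
| 0.33, 0.25 | 83.8–84.8% |

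The gain is about 0.4 to 5 points. Over this range the log-odds SE rises from 0.196 to 0.197–0.212, while the estimate moves from 0.548 to 0.553–0.634. The power comes from the larger conditional effect. On the risk-difference scale the variance falls by about 1% to 13.5%.

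**3. Racial gap.** Spurious shift = imbalance in the factor between races × difference in surgery rate with and without the factor. Assumptions: the factor is present in 25% of the reference group, whose surgery rate is 0.66 (the previous-study rate for white patients in SAP section 7).

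- Odds ratio 0.7: rates 0.681 and 0.599, difference 0.082. A 5-point imbalance gives 0.05 × 0.082 = 0.4 points.
- Odds ratio 0.25: rates 0.741 and 0.417, difference 0.324. A 20-point imbalance gives 0.20 × 0.324 = 6.5 points.
- No imbalance: 0 points.

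The gap in the previous study was 0.66 − 0.55 = 11 points.

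**4. Surgical versus non-surgical outcomes.** The documents give no survival or SF-12 figures by stage or entry route, so this bias cannot be calculated. The argument is structural: the protocol ties entry route to resection, and a benign or malignant lesion and its stage plausibly bear on outcome.

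**5. Room in the model.** The limiting count is non-surgery: 496 × 0.37 ≈ 184 patients. The SAP allows 30–35 main effects, which is 184/30 = 6.1 down to 184/35 ≈ 5.2 per term (183.5/35 before rounding). Adding two to 35 gives 184/37 = 5.0.

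**The case against.** **The list is open.** The SAP says covariates will include these items, asks for as large a maximum model as possible, and names 14 of a possible 30–35. It would be wrong to infer that the plan rules these variables out. What stands against the plan is that neither is pre-specified, an unforced term can be dropped by its p-value, and the survival comparison names no covariates.

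**The arm effect.** A reader might infer that the omission biases the randomised comparison or enlarges its standard error. It does neither. If allocation is sound, the overall arm effect and the within-race arm effects relevant to hypothesis 2c are not confounded by these variables, and the log-odds standard error does not fall on adjustment.

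**Stage and surgery.** No section says that stage I versus II changes the chance of surgery. The maximal-rate analysis under hypothesis 1b removes non-surgical patients needing pneumonectomy or multiple lobectomy, which suggests that tumour extent matters, but that is not a statement about stage.

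**Tissue and surgery.** The refusal remark concerns some patients, partly identified by lung disease, so forced comorbidity captures part of it. Section E.1 also says that many proceed to surgery without a tissue diagnosis. Section C still supports lower surgery rates without tissue, but gives no size.

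**Race.** Protocol section E.2 mentions late presentation among African-Americans. That concerns lung cancer overall, not stage I versus II among eligible patients, so it does not document an imbalance.

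**Data.** The questionnaire lists neither item, and the UNC clinic list shows stage only where determined. A data-capture item may therefore be needed.

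**Conclusion.** The point holds in a limited form. Two facts required for eligibility, one of them tied to surgery by the protocol, are neither named nor forced in the Aim 1, survival or Aim 4 analyses. The case is strongest for survival and SF-12 by surgical status, where confounding is likely but of unknown size and direction. For racial gaps, confounding is possible: about 0.4 to 6.5 points under assumed imbalances of 5 to 20 points and odds ratios of 0.7 to 0.25, and zero without imbalance. For the randomised comparison the only loss is modest power, about 0.4 to 5 points under assumed shares and effects.

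Adjustment would reduce the confounding, not remove it. Among probability-only patients, those not resected may still include benign lesions that the entry variable cannot separate.

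**What to change.** - Record clinical stage (I or II) and entry route (tissue proven or probability only) for every patient at enrolment.
- Name both as forced baseline predictors in the Aim 1 model and in the Aim 4 SF-12 models.
- Add a covariate-adjusted survival model containing both, alongside the Kaplan-Meier curves.
- Report both variables by arm and by race.

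The cost is a small data-capture item, a few lines of SAP text and two model terms. With about 184 non-surgical patients, those terms should replace weaker candidates. Patient satisfaction is one: protocol section E.3 first lists it at the 6-month interview, after the 4-month window for the primary outcome.
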